2.2.4 Sample Size Determination

The primary efficacy endpoint of this study is the proportion of subjects who progress to death or respiratory failure by the end of study (Day 28). It is estimated that approximately 30% of enrolled subjects receiving SOC plus placebo will attain this endpoint. It is assumed that losmapimod will improve the primary endpoint by 40% over placebo. On the basis of these assumptions, a total of up to 410 subjects randomized to the losmapimod arm or the placebo arm in a 1:1 ratio (205 subjects in the losmapimod arm and 205 subjects in the placebo arm) will yield approximately 80% power in a 1-sided test at the 2.5% significance level.

The sample size estimate assumes an IA will be conducted after approximately 206 subjects (103 in the losmapimod arm, and 103 in the placebo arm) have completed the Day 28 visit, to assess early futility, using the rules specified in Section 5.1.

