3 STATISTICAL METHODOLOGY

3.1 General Considerations

3.1.1 *Analysis Day*

Analysis day will be calculated from the date of first dose of study drug. The day of the first dose of study drug will be Day 1, and the day immediately before Day 1 will be Day -1. There will be no Day 0.

3.1.2 *Definition of Baseline*

Baseline is defined as the last measurement prior to the first dose of study drug.

3.1.3 *Summary Statistics*

Categorical data will generally be summarized with counts and percentages of subjects. The denominator used for the percentage calculation will be clearly stated. Continuous data will generally be summarized with descriptive statistics including n (number of non-missing values), mean (with its standard error), first quartile, median, third quartile, standard deviation, minimum, and maximum.

Where appropriate, descriptive statistics may be presented with 95% CI.

3.1.4 *Hypothesis Testing*

All statistical comparisons will be made using one-sided tests at $\alpha = 0.025$. All null hypotheses will be of no treatment difference, and all alternative hypotheses will be one-sided. Confidence intervals will be 2-sided with $\alpha = 0.05$ and reported to the same precision as the applicable summary statistic (e.g., mean), and standard error will be reported to one additional decimal place. P-values will be reported to four decimal places, with p-values less than 0.0001 reported as "<0.0001".

3.1.5 *Type I Error for Testing Key Study Endpoints*

The overall Type I error of the study will be controlled at 0.025 for 1-sided tests of hypotheses for the following key study endpoints, using a closed test procedure. The key endpoints will be tested in the fixed sequence procedure as the same sequence they are listed below. Assuming the analysis of the prior endpoint yields statistically significant treatment effect, the next key endpoint will be tested.

1. Proportion of progressors to death or respiratory failure by Day 28
2. Change in clinical status using the 9-point WHO scale at Day 14
3. Change in clinical status using the 9-point WHO scale at Day 7
4. Oxygen-free days by Day 28

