3.4 Efficacy Assessment

3.4.1 Primary Efficacy Endpoint

3.4.1.1 Primary Analysis

The primary efficacy endpoint is the proportion of subjects who progress to death or respiratory failure by Day 28.

Respiratory failure is defined as either need for mechanical ventilation (invasive or non-invasive) or high flow oxygen (defined by greater than 15 LPM flow of oxygen to maintain oxygen saturation between 90% and 95%), sustained for at least 48 hours, at any time during the study.

The fitted logistic regression model is used to predict the response rate for every subject in the study as if they had received the treatment or the control intervention.

Assuming p_t is probability of outcome in the losmapimod arm; p_c is the probability of outcome in the control arm

Study hypothesis: $H_0: p_t - p_c = 0$

$H_1: p_t - p_c < 0$

Assuming $p_t=0.18$, $p_c=0.30$, we can restate the hypothesis as

$H_0: \theta = \theta_0 = 0$

$H_1: \theta = \theta_1 = -0.12$

where θ is calculated as $p_t - p_c$. For the final analysis, the proportion of subjects achieving the primary endpoint in the treatment arms will be compared using an adjusted risk difference obtained from the logistic regression model, adjusted for stratification factors, sex, and baseline CRP. Sample SAS codes are provided in Appendix A. More details can be found in Guo et al. (2012) and Ge et al. (2011).

An interim analysis to assess futility analysis—and potential sample size re-estimation—will be conducted, as discussed in Section 5.1.

All results will be summarized descriptively by treatment arm and expressed as proportions, along with corresponding unadjusted/adjusted 95% CI of the difference between response rates, and p-values.

In the first step of multiple imputation, data will be multiple imputed using the FCS discriminant function separately by treatment arm to 20 imputed datasets. This analysis assumes data are missing at random. The imputation model will include the stratification factors, sex, baseline CRP, and a two-level binary factor (discharge from the hospital prior to discontinuing the study; Yes, No). [REDACTED]

For each imputed dataset, the proportion of subjects achieving the primary endpoint in the treatment arms will be compared using an adjusted risk difference obtained from the logistic regression model, adjusted for stratification factors, sex, and baseline CRP for each imputed dataset.

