The estimated treatment effect and associated standard errors from each imputation from the 20 logistic regression model will be combined using Rubin's rules to provide an overall treatment effect, associated 95% confidence interval (CI), and 2-sided p-value. Sample codes are listed below.

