5 ANALYSIS TIMING

5.1 Interim Analysis

An IA will be conducted after 206 subjects have been enrolled (approximately 103 in each of the losmapimod and placebo arms) and have been treated for 14 days with 28 days of follow-up. Only futility—and potential sample size-estimation—will be assessed by the DMC at the IA. The O'Brien-Fleming group sequential method will be used to adjust alpha and beta for interim testing. Table 2, Figure 1, Figure 2, and Figure 3 contain sample size requirements, boundary information, and stopping probabilities for testing futility on the primary endpoint at both the IA and final analysis. P -values are single-sided. Sample size estimation was done using SAS® (Proc SeqDesign, Version 4.0). The study will not be stopped for efficacy at the IA.

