5.1.1 Futility Testing

The process is as follows:

1. Futility at IA: If standardized z-value (MLE: maximum likelihood estimate) of $p_t - p_c$ is ≥ -0.67873 (-0.04017), or p-value ≥ 0.24865 , then stop for futility. Probability of stopping for futility under null hypothesis is ~ 0.75 .
2. At Final Analysis: The final p-value is tested at an adjusted alpha of 0.02784.

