| Final Analysis | 205 | 205 | -1.91358 (0.02784) | -0.08009 | 0.97500 | -- | -- | 0.20000 |

Overall alpha=0.025 (1-sided); overall power=80%.

Abbreviations: MLE: maximum likelihood estimate.

Figure 1 Acceptance Region (Standardized-Z Scale)

[figure not shown]

Figure 2 Acceptance Region (P-value)

[figure not shown]
[figure not shown]

Figure 3 Acceptance Region (Maximum Likelihood Estimate)

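### SAP 3.4.1.1 gives the primary pooled analysis a 2-sided p-value within a one-sided testing framework, and no visible text says which p-value Section 5.1.1 tests

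*SAP*

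**What the plan says.** SAP 3.4.1.1 fits a covariate-adjusted logistic model in each of 20 imputed datasets and combines the risk differences and standard errors by Rubin's rules "to provide an overall treatment effect, associated 95% confidence interval (CI), and 2-sided p-value". In the text supplied, this is the only sentence that states the sidedness of the primary analysis p-value.

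The rest of the framework is one-sided:

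- SAP 3.1.4: "All statistical comparisons will be made using one-sided tests at" 0.025. The same subsection adds "Confidence intervals will be 2-sided with" alpha 0.05, so 2-sided intervals alongside one-sided tests are deliberate.
- SAP 3.1.5 controls the fixed sequence of four key endpoints at one-sided 0.025.
- SAP 3.4.1.1 states the alternative as p_t - p_c < 0.
- SAP 2.2.4: the sample size "will yield approximately 80% power in a 1-sided test at the 2.5% significance level".
- SAP 5.1, introducing the boundaries, says that P "values are single-sided".
- The footnote to Table 2 reads "Overall alpha=0.025 (1-sided); overall power=80" (percent).

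SAP 5.1.1 sets the decision rule: "The final p-value is tested at an adjusted alpha of 0.02784". It does not say which p-value that is, and it does not refer back to the pooled analysis in 3.4.1.1.

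**The concern.** The primary endpoint decides whether the trial succeeds, and under the fixed sequence it is the gate to the other three key endpoints. Its analysis section names one kind of p-value, while its decision threshold is calibrated for the other. In Table 2, 0.02784 stands beside z = -1.91358, and that is a single-tail probability.

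For the same data, the 2-sided p-value is twice the one-sided value when the estimate favours losmapimod. A pooled 2-sided p of 0.040 in that direction is a one-sided 0.020. That passes at 0.02784, whereas 0.040 does not. A plan should leave only one verdict for any dataset, and the choice between these two should not have to be argued after unblinding. SAP 3.4.2 does fix the sidedness for oxygen-free days, but 3.4.1.1 has no matching statement for the primary test.

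**Working it through.** **Inputs.** From SAP Table 2: interim boundary z = -0.67873 (difference -0.04017) and final boundary z = -1.91358 (difference -0.08009). From SAP 3.4.1.1: p_t = 0.18, p_c = 0.30, difference -0.12. From SAP 2.2.4: 103 per arm at the interim and 205 per arm at the end.

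**Step 1: standard errors implied by Table 2.**
- Interim: 0.04017 / 0.67873 = 0.05918.
- Final: 0.08009 / 1.91358 = 0.04185.
- Information fraction: (0.04185 / 0.05918)² = 0.500, so the correlation between the interim and final z is √0.500 = 0.707.
- Mean z under the design alternative: -0.12 / 0.05918 = -2.028 at the interim and -0.12 / 0.04185 = -2.867 at the end.

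**Step 2: reproduce the plan.** Success requires Z1 < -0.67873 and Z2 < b, with (Z1, Z2) bivariate normal. With b = -1.91358:
- probability of stopping for futility under the null: 0.7513 (Table 2: 0.75135);
- one-sided type I error: 0.0250 (stated 0.025);
- power: 0.800 (stated 80%).

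The plan's figures reproduce for a one-sided p-value tested at 0.02784.

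**Step 3: change only the p-value that is compared.** A 2-sided p of 0.02784 is a single tail of 0.02784 / 2 = 0.01392, so |z| must reach 2.200. A 2-sided p of 0.025 needs |z| of 2.241, and one of 0.05 needs 1.960.

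| Final comparison | Bound on z | Power | One-sided type I error |
|---|---|---|---|
| One-sided p against 0.02784 | -1.914 | 80.0% | 0.0250 |
| 2-sided p against 0.02784 | -2.200 | 72.9% | 0.0130 |
| 2-sided p against 0.025 | -2.241 | 71.7% | 0.0118 |
| 2-sided p against 0.05 | -1.960 | 79.0% | 0.0226 |

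Binomial variances at 103 and 205 per arm, used in place of the Table 2 standard errors, give 80.2% falling to 73.1% (unpooled) or 79.5% falling to 72.2% (pooled) for the first two rows.

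**Step 4: where the first two rows disagree.** They give opposite verdicts for a final z between -2.200 and -1.914. On other scales:
- 2-sided p between 0.02784 and 2 × 0.02784 = 0.05568;
- observed difference between -2.200 × 0.04185 = -0.092 and -1.914 × 0.04185 = -0.080.

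Under the design alternative this has probability 80.0% - 72.9% = 7.1%.

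**The case against.** The strongest reply is that no passage tells anyone to compare the 2-sided p-value with 0.02784, and that several passages rule it out. SAP 3.1.4 makes every comparison one-sided, 5.1 declares the boundary p-values single-sided, and Table 2 pairs the threshold with a signed z and a signed difference. Protocol 8.1.1, 8.6, 8.9 and 8.11 agree. On this view the sentence in 3.4.1.1 only lists reported output: a 2-sided p-value beside a 2-sided interval. With the sign of the estimate known, the one-sided value follows directly. The sample code to which 3.4.1.1 refers is not in the supplied text and may contain the conversion; its absence here is not a defect of the plan.

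Most of this stands. It settles the more likely reading, and it means that the 73% is not a property of the planned test. It does not remove the conflict. The one sentence on the pooled p-value still says 2-sided, and 5.1.1 still does not say which p-value it tests.

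A reader might also infer that a harmful effect could meet a 2-sided criterion. The documents do not support that. The alternative is directional, a positive estimate cannot cross z = -1.91358 or a difference of -0.08009, and the interim rule stops the trial at z of -0.67873 or above.

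**Conclusion.** The inconsistency is real and sits in the primary decision rule, but it is an error of wording. A reader might infer that the trial, run exactly as written, has 73% power. That does not follow, because it requires the 2-sided value to be taken as the final p-value against SAP 3.1.4 and 5.1. The planned properties remain 80% power and 2.5% one-sided error, the latter only if the futility stop is binding; otherwise the error at this threshold is 0.0278.

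The cost of the misapplication is about 7 points of power and a one-sided error of about 1.3%. It would be conservative: it creates no false positives but could turn a planned success into a failure. These figures use a normal approximation with the design's event rates. They leave out sample size re-estimation, dropout, imputation variance and covariate adjustment.

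This should be fixed as a wording correction; it is not a demonstrated loss of power.

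**What to change.** In SAP 3.4.1.1, replace the 2-sided p-value with *a one-sided p-value for H1: p_t - p_c < 0, computed from the pooled estimate and pooled standard error*. State that this is the final p-value tested under 5.1.1. Keep the 2-sided 95% confidence interval for estimation, and label any 2-sided p-value as descriptive. The interval should not serve as the decision rule, because it excludes zero at |z| of 1.960 whereas the final boundary is 1.914.

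This costs a few lines of SAP text before unblinding. No boundary, sample size or analysis model changes.

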3.4.2 Secondary Efficacy Endpoints

Clinical status at Day 7 and Day 14:

Change in clinical status between baseline and at Days 7 and 14 will be modeled using ordinal logistic regression models, adjusting for stratification factors, sex and baseline CRP. If the subject progresses to death and the value of WHO 9-point scale is missing, the missing value of WHO 9-point will be imputed as (8) death.

Percentages for each category of the ranking scale will be tabulated by treatment arm, along with differences between treatment arms at each time point. The proportion of subjects for each of the items in the scale will be compared using an adjusted risk difference obtained from an ordinal logistic regression model, adjusting for stratification factors, sex and baseline CRP.

Total number of study days by Day 28:

(a) Free of oxygen supplementation; (b) in ICU; (c) of hospitalization; (d) free of respiratory failure; (e) alive; For each endpoint (a) – (e), a Poisson regression model will be used to assess

the relationship with treatment, adjusting for stratification factors, sex, baseline CRP and number of days on study. The key study endpoint of “oxygen free days by Day 28” will be tested at 1-sided significance level of 0.025 as outlined in Section 3.1.5.

If a patient died, the number of days of (a)-(e) are considered as having the events on and after the patient died. For example, if a patient died on Day 6. The days from Day 6 and after are considered not free of oxygen supplementation, hospitalization, ICU, and respiratory failure.

Percentage of subjects discharged from the hospital by Day 28:

Percentages of subjects discharged from the hospital will be tabulated by treatment arm, along with differences between treatment arms. The proportion of subjects will be compared using an adjusted risk difference obtained from a logistic regression model, adjusting for stratification factors, sex, and baseline CRP.

The percentage of subjects discharged from the hospital is defined as the number of subjects discharged from the hospital divided by the sum of the number of subjects who completed the study and the number of subjects who died during the study period.

A sensitivity analysis will be performed by excluding the subjects who died after being discharged from the hospital from the numerator of the above percentage calculation.

Missing data will be imputed similarly as primary endpoint for the above endpoints.

All-cause mortality at Day 28:

Percentages of subjects will be tabulated by treatment arm, along with differences between treatment arms, at each time point. The proportion of subjects will be compared using an adjusted risk difference obtained from a logistic regression model, adjusting for stratification factors, sex, and baseline CRP.

Standard survival analysis methods will be used as sensitivity analyses to compare the time to each of these clinical events of interest (death and respiratory failure) as well as the composite thereof. Specifically, the cumulative incidence rates between two groups at Day 28 will be compared, accounting for potential differential follow-up.

Incidence of AEs/SAEs by Day 28: will be summarized by system organ class and preferred term and by treatment arm using percentages.

Incidence of AEs/SAEs is calculated by the number of subjects who developed AEs/SAEs during the study divided by the sum of the number of subjects who completed the study and the number of subjects who died during the study period. (see above edit)

Incidence of clinically significant changes by Day 28: Percentage of subjects with clinically significant changes in laboratory parameters, ECG, and vital sign measurements will be computed for each treatment arm along with associated 2-sided 95% Clopper-Pearson CI.

Changes in the assessments will be considered as clinically significant if the Baseline assessment is not clinically significantly abnormal and there has been at least one occurrence of post-Baseline assessments with a clinically significant abnormal result by Day 28.

[figure not shown]
Death is not considered a form of missing data or censoring. The incidence of clinically significant changes is calculated by the number of subjects with clinically significant changes during the study divided by the sum of the number of subjects who completed the study and the number of subjects who died during the study period.

Clearance of quantifiable viral RNA by Day 7: percentages of subjects with clearance of quantifiable viral RNA will be tabulated by treatment arm, along with differences between treatment arms, at each time point. The proportion of subjects will be compared using an adjusted risk difference obtained from a logistic regression model, adjusting for stratification factors, sex, and baseline CRP.

Change from baseline in viral RNA will be summarized by treatment arm and also analyzed using an analysis of covariance (ANCOVA) model with fixed effects of treatment, and stratification factors, sex and baseline CRP as covariates.

Death is not considered a form of missing data or censoring. The proportion of subjects with clearance of quantifiable viral RNA by Day 7 is calculated by the number of subjects with clearance of quantifiable viral RNA by Day 7 divided by the sum of the number of subjects who is in study by Day 7 and the number of subjects died by Day 7.

The endpoint of comparing percentage of subjects discharged from the hospital, all-cause mortality by Day 28, incidence of AEs/SAEs, incidence of clinically significant changes, and percentage of subjects with clearance of quantifiable viral RNA by Day 7 between treatment groups will be analyzed similarly as the primary endpoint.

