4 STUDY POPULATION

4.1 Inclusion criteria

Eligible subjects must meet all of the following inclusion criteria at screening.

1. Able and willing to provide written informed consent.
 - a. Note: Subject's legally authorized representative may provide informed consent as applicable based on local guidelines and regulations (see [Section 9.1.3](#)). If consent is obtained from a legally authorized representative, then assent should be obtained from the subject.
2. Willing and able to comply with all study procedures.
3. Age ≥ 40 years at time of screening.
4. Confirmed infection with SARS-CoV-2 virus at or before the baseline visit (by polymerase chain reaction [PCR] testing).
 - a. Note: Refer to the Study Manual for details on PCR SARS-CoV-2 testing procedures.
5. ≤ 7 days to the time of randomization from the time of collection of the specimen that tested positive for the SARS-CoV-2 virus.
6. Hospitalization at the time of the baseline visit.
7. Oxygen saturation $\geq 92\%$ at the baseline visit, which can be either on room air or on oxygen supplementation if using $\leq 10\text{LPM}$ by nasal prong or close-fitting mask.
8. Evidence of pulmonary involvement consistent with COVID-19 by either clinical examination or radiographic examination (whichever is per local standard of care), per the judgment of the investigator. Evidence of pulmonary involvement obtained by clinical examination should be documented in the eCRF.
9. Clinical syndrome consistent with COVID-19 at screening, per the judgment of the investigator ([CDC 2020](#)).
10. CRP at screening $>15 \text{ mg/L}$ (which is equivalent to $>1.5 \text{ mg/dL}$) on local laboratory testing.
11. Agrees to practice an approved method of birth control as follows (as applicable to local [country] guidelines and regulations for sites outside the US):
 - a. Females of childbearing potential: Using 1 of the following acceptable methods of contraception: surgical sterilization (eg, bilateral tubal ligation), intrauterine contraception/device, hormonal contraception, or any 2 barrier methods (a combination of male or female condom with diaphragm, sponge, or cervical cap). This criterion must be followed from the time of the first dose of study medication until 90 days after last dose

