2 STUDY OVERVIEW

2.1 Objectives and Endpoints

| Objectives | Endpoints |
|---|--|
| Primary | |
| To assess the efficacy of losmapimod compared with placebo for treatment of COVID-19 when administered concurrently with standard of care | Proportion of progressors to death or respiratory failure by Day 28 |
| Secondary | 
To evaluate the effect of losmapimod compared with placebo on clinical outcomes
 
Clinical status by Days 7 and 14 as measured on the 9-point WHO ordinal scale:
 
• (8) death• (7) ventilation plus additional organ support (vasopressors, renal replacement therapy, ECMO)• (6) Intubation and mechanical ventilation• (5) noninvasive ventilation or high-flow oxygen therapy• (4) oxygen therapy but not requiring high-flow or non-invasive ventilation• (3) hospitalized but not requiring oxygen therapy• (2) Discharged from the hospital but with limitation of activities |

| | |
|---|---|
| | 
• (1) Discharged from the hospital and without any limitation• (0) No clinical evidence of the disease |
| To assess the effect on clinical status of treatment with losmapimod compared with placebo | Total number of study days free of oxygen supplementation by Day 28 Total number of study days in ICU by Day 28 Total number of study days hospitalized by Day 28 Total number of respiratory failure-free study days by Day 28 Percentage of subjects discharged from the hospital by Day 28 |
| To assess the effect on survival following treatment with losmapimod compared with placebo | All-cause mortality at Day 28 Number of study days alive by Day 28 |
| To assess the safety and tolerability of losmapimod compared with placebo | Incidence of AEs and SAEs Incidence of clinically significant changes in laboratory parameters and vital sign measurements |
| To characterize changes in SARS-CoV-2 infection following treatment with losmapimod compared with placebo | Quantifiable viral RNA on Day 7 |
| | |

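### Key endpoints 2 and 3 analyse change in the WHO score, which ranks some deaths level with survival on organ support; modelling the score itself would always rank death worst

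*SAP*

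**What the plan says.** SAP 3.1.5 states: "The overall Type I error of the study will be controlled at 0.025 for 1-sided tests of hypotheses", by a fixed sequence. After the primary endpoint come "Change in clinical status using the 9-point WHO scale at Day 14" and then "Change in clinical status using the 9-point WHO scale at Day 7". SAP 3.4.2 gives the analysis: "Change in clinical status between baseline and at Days 7 and 14 will be modeled using ordinal logistic regression models", adjusted for the stratification factors (age group and oxygen requirement), sex and baseline CRP. Protocol 8.7 and 8.11 also speak of change. The objectives table (SAP 2.1) names something different: "Clinical status by Days 7 and 14 as measured on the 9-point WHO ordinal scale".

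The scale runs from 0 to 8, with death at 8. The level below it is "7) ventilation plus additional organ support (vasopressors, renal replacement therapy, ECMO", and a subject on low-flow oxygen is at "4) oxygen therapy but not requiring high-flow or non-invasive ventilation". A subject in hospital without oxygen is at 3. Protocol 4.1 requires hospitalisation at baseline and an adequate saturation, "which can be either on room air or on oxygen supplementation", with oxygen at no more than 10 LPM. Exclusion criterion 2 removes critical disease and immediate need for ventilation. Baseline scores are therefore essentially 3 or 4.

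For death, SAP 3.4.2 fills a missing WHO score with 8. Neither document says how death ranks once baseline has been subtracted, and neither defines change.

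**The concern.** Death is placed at the top of the scale so that it is always the worst result. Subtracting a baseline that can be 3 or 4 undoes this. Deaths are split over two levels of the new variable, and the larger baseline group's deaths may share a level with survivors. Most other levels also lose a single clinical meaning. At +1, a subject who starts low-flow oxygen (3 to 4) equals one who moves to noninvasive ventilation or high-flow oxygen (4 to 5), a state that can count as respiratory failure in the primary endpoint if sustained. At -1, discharge with limitation (3 to 2) equals remaining in hospital off oxygen (4 to 3).

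At stake is what an alpha-controlled odds ratio would mean. A reader told that losmapimod shifts the odds by one level could not say which clinical states that separates without knowing each subject's baseline.

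**Working it through.** **The plan's own figure.** The SAP gives no power or sample size for key endpoints 2 and 3. The only design figure is about 80% power for the primary endpoint with 205 per arm (0.30 versus 0.18, one-sided 0.025). With pooled variance under the null:

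- null SE = sqrt(2 × 0.24 × 0.76 / 205) = 0.0422
- alternative SE = sqrt((0.30 × 0.70 + 0.18 × 0.82) / 205) = 0.0418
- power = Φ((0.12 - 1.96 × 0.0422) / 0.0418) = 0.814, or 0.802 with the stated futility boundary

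This reproduces the plan's figure, but nothing below depends on it.

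**Enumeration.** Change = score at Day 7 or 14 minus baseline score. The body of the table gives the WHO score at follow-up.

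| Change | From baseline 3 | From baseline 4 |
|---|---|---|
| -4 | none | 0 |
| -3 | 0 | 1 |
| -2 | 1 | 2 |
| -1 | 2 | 3 |
| 0 | 3 | 4 |
| +1 | 4 | 5 |
| +2 | 5 | 6 |
| +3 | 6 | 7 |
| +4 | 7 (alive) | 8 (death) |
| +5 | 8 (death) | none |

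There are ten levels. Eight of them (-3 to +4) each hold two different clinical states. The pair 3 to 7 and 4 to 8 is the only one in which a survivor equals a death. Within either column death is strictly the worst.

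**Share of deaths coded +4.** Let f be the proportion on oxygen, and d4 and d3 the Day 14 mortality from baselines 4 and 3. The share is f × d4 / (f × d4 + (1 - f) × d3). The documents give none of these. Assuming d4 = 7% and d3 = 3%:

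- f = 40%: 0.028 / (0.028 + 0.018) = 61%
- f = 60%: 0.042 / (0.042 + 0.012) = 78%
- f = 80%: 0.056 / (0.056 + 0.006) = 90%

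**Survivors in the tie.** With f = 60%, 0.40 × 410 = 164 subjects enter off oxygen. If 1% to 3% of them are alive at score 7 (an assumption), that is about 2 to 5 subjects.

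**Effect on the estimate.** These are simulated trials of 410 subjects. In the first set, 70% were on oxygen and the common odds ratio was 1.6 (log 0.470). The assumed placebo Day 14 probabilities for scores 0 to 8 were 0.15, 0.30, 0.18, 0.15, 0.08, 0.04, 0.03, 0.03, 0.04 from baseline 3, and 0.08, 0.25, 0.17, 0.10, 0.15, 0.07, 0.05, 0.05, 0.08 from baseline 4. Results over 40 trials:

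| Model | Mean log OR | Power |
|---|---|---|
| Change, oxygen factor in | -0.465 | 0.725 |
| Change, oxygen factor out | -0.459 | 0.700 |
| Status, oxygen factor in | -0.470 | 0.750 |

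The Monte Carlo standard error of each power is about 7 points, so the powers cannot be told apart. With no treatment effect, the three mean log odds ratios were 0.039 to 0.043, again indistinguishable.

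A set of 149 trials under assumed distributions gave -0.388 for change and -0.395 for status. About 98% of the information was kept, and about 97% with the oxygen factor dropped. In a further 240 trials (log odds ratio -0.40), the ratio of squared mean z, change to status, was 0.974 to 0.988 over four runs of 60. A loss of 1.2% to 2.6% corresponds to about 5 to 11 of 410 subjects.

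**The case against.** The strongest reply is that the model already conditions on baseline. Oxygen requirement at randomisation is a stratification factor and a covariate, and with entry limited to 3 or 4 it is nearly the baseline WHO score. Within an oxygen stratum, change is status minus a constant, so the ordering there is untouched. This stands, and it explains why the estimate barely moves. It is not guaranteed, because SAP 3.1.7 allows stratification factors to be removed if the model does not converge. Even then the loss in simulation was small.

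Second, status is also analysed. The next paragraph of SAP 3.4.2 tabulates each category of the scale and compares categories by adjusted risk difference. Mortality has its own analysis, and death is part of the primary endpoint, which must succeed first. All of this is correct, but none of it is the test listed as key endpoint 2 or 3.

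Third, the SAP text never states that change is a subtraction. That is the natural reading, but the programming specifications, which are a separate document, may say otherwise. The point depends on this reading.

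A reader might go further and infer that the odds ratio cannot be interpreted at all, that the test is invalid, or that survivors can rank worse than the dead. The documents do not support this. No eligible survivor scores above a death. With no treatment effect, change has the same distribution in both arms, so the test keeps its level. The simulations show no material bias.

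**Conclusion.** The concern holds as one of ranking and interpretability. On the score-difference reading, a death from baseline 4 ties at +4 with a survivor at score 7 who was enrolled off oxygen, and only deaths from baseline 3 reach the worst level. Under the stated mortality assumptions, about 61% to 90% of deaths sit one level below the worst. That percentage describes the coding and is not the size of any error in the treatment effect: few survivors share the level, bias is negligible and about 98% of the information is kept. The simulation figures rest on assumed Day 14 distributions and proportional odds.

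The change is still worth making. The listed objective is clinical status, the SAP itself assigns death the top score, and a claim within the alpha-controlled sequence should rest on a scale where death is always worst and each level has one meaning. This is a recommended improvement and is not a condition for a valid trial.

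**What to change.** Make the key analysis for items 2 and 3 a proportional-odds model of the WHO score itself at Day 14 and at Day 7, with death (8) as the worst category. Adjust for baseline WHO score, age stratum, sex and baseline CRP. Baseline score should replace the oxygen factor, or the two should be checked for redundancy, since they nearly coincide. If a covariate then has to be dropped for non-convergence, death still ranks worst.

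Rename items 2 and 3 of SAP 3.1.5 as clinical status at Day 14 and Day 7, and align SAP 3.4.2. Because protocol 8.7 and 8.11 also say change, record the departure in SAP section 6 before the interim analysis, by which time the SAP is to be final.

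The data, the type of model and the sample size stay the same, and no power is lost. The cost is a documented departure from the protocol wording. If the sponsor prefers to keep change, the minimum is to define it and to state that death takes the worst rank whatever the baseline.
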